9.4.6 Methods for multiplicity control

No multiplicity adjustment will be applied.

9.5 Interim analyses

Interim analyses are not planned in this study

11 SUPPORTING DOCUMENTATION AND OPERATIONAL CONSIDERATIONS

Appendix A Regulatory, ethical and study oversight considerations

A 1 Regulatory and ethical considerations

This study will be conducted in accordance with the protocol and with the following:

- Consensus ethical principles derived from international guidelines including the Declaration of Helsinki and Council for International Organizations of Medical Sciences (CIOMS) International Ethical Guidelines
- Applicable International Conference on Harmonisation (ICH) Good Clinical Practice (GCP) Guidelines
- Applicable laws and regulations

The protocol, protocol amendments, ICF, Investigator Brochure, and other relevant documents (e.g., advertisements) must be submitted to an IRB/ independent ethics committee (IEC) by the investigator and reviewed and approved by the IRB/IEC before the study is initiated.

Any amendments to the protocol will require IRB/IEC approval before implementation of changes made to the study design, except for changes necessary to eliminate an immediate hazard to study subjects.

The investigator will be responsible for the following:

- Providing written summaries of the status of the study to the IRB/IEC annually or more frequently in accordance with the requirements, policies, and procedures established by the IRB/IEC
- Notifying the IRB/IEC of SAEs or other significant safety findings as required by IRB/IEC procedures
- Providing oversight of the conduct of the study at the site and adherence to requirements of 21 CFR, ICH guidelines, the IRB/IEC, European regulation 536/2014 for clinical studies (if applicable), and all other applicable local regulations

The study will be performed in accordance with the AstraZeneca policy on Bioethics and Human Biological Samples.

A 2 Financial disclosure

Investigators and sub-investigators will provide the sponsor with sufficient, accurate financial information as requested to allow the sponsor to submit complete and accurate financial certification or disclosure statements to the appropriate regulatory authorities. Investigators are responsible for providing information on financial interests during the course of the study and for 1 year after completion of the study.

A 3 Informed consent process

The investigator or his/her representative will explain the nature of the study to the subject or his/her legally authorised representative and answer all questions regarding the study.

Subjects must be informed that their participation is voluntary. Subjects or their legally authorised representative will be required to sign a statement of informed consent that meets the requirements of 21 CFR 50, local regulations, ICH guidelines, Health Insurance Portability and Accountability Act (HIPAA) requirements, where applicable, and the IRB/IEC or study centre.

The medical record must include a statement that written informed consent was obtained before the subject was enrolled in the study and the date the written consent was obtained. The authorised person obtaining the informed consent must also sign the ICF.

Subjects must be re-consented to the most current version of the ICF(s) during their participation in the study.

A copy of the ICF(s) must be provided to the subject or the subject's legally authorised representative.

If a subject's partner becomes pregnant from starting the investigational product administration until 90 days after the last dose of investigational product, the partner is asked to sign the "Adult Study Informed Consent Form for Pregnant Partners of Study Subjects" and provide information about the pregnancy accordingly.

Subjects who are rescreened are required to sign a new ICF.

A 4 Data protection

Each subject will be assigned a unique identifier by the sponsor. Any subject records or data sets transferred to the sponsor will contain only the identifier; subject names or any information which would make the subject identifiable will not be transferred.

The subject must be informed that his/her personal study-related data will be used by the sponsor in accordance with local data protection law. The level of disclosure must also be explained to the subject.

The subject must be informed that his/her medical records may be examined by Clinical Quality Assurance auditors or other authorised personnel appointed by the sponsor, by appropriate IRB/IEC members, and by inspectors from regulatory authorities.

A 5 Committees structure

Data monitoring committee will not be set.

A 6 Dissemination of clinical study data

A description of this clinical trial will be available on <http://astrazenecaclinicaltrials.com> and <http://www.clinicaltrials.gov> as will the summary of the study results when they are available. The clinical trial and/or summary of study results may also be available on other websites according to the regulations of the countries in which the study is conducted.

A 7 Data quality assurance

All subject data relating to the study will be recorded on printed or electronic CRF unless transmitted to the sponsor or designee electronically (e.g., laboratory data). The investigator is responsible for verifying that data entries are accurate and correct by physically or electronically signing the CRF.

The investigator must maintain accurate documentation (source data) that supports the information entered in the CRF.

The investigator must permit study-related monitoring, audits, IRB/IEC review, and regulatory agency inspections and provide direct access to source data documents.

The sponsor or designee is responsible for the data management of this study including quality checking of the data.

Study monitors will perform ongoing source data verification to confirm that data entered into the CRF by authorised site personnel are accurate, complete, and verifiable from source documents; that the safety and rights of subjects are being protected; and that the study is being conducted in accordance with the currently approved protocol and any other study agreements, ICH GCP, and all applicable regulatory requirements.

Records and documents, including signed ICFs, pertaining to the conduct of this study must be retained by the investigator for 15 years after study completion unless local regulations or institutional policies require a longer retention period. No records may be destroyed during the retention period without the written approval of the sponsor. No records may be transferred to another location or party without written notification to the sponsor.

A 8 Source documents

Source documents provide evidence for the existence of the subject and substantiate the integrity of the data collected. Source documents are filed at the investigator's site.

Data reported on the CRF that are transcribed from source documents must be consistent with the source documents or the discrepancies must be explained. The investigator may need to request previous medical records or transfer records, depending on the study. Also, current medical records must be available.

Definitions of what constitutes source data can be found in Clinical Study Agreement and/or other documents.

A 9 Publication policy

The results of this study may be published or presented at scientific meetings. If this is foreseen, the investigator agrees to submit all manuscripts or abstracts to the sponsor before submission. This allows the sponsor to protect proprietary information and to provide comments.

The sponsor will comply with the requirements for publication of study results. In accordance with standard editorial and ethical practice, the sponsor will generally support publication of multicentre studies only in their entirety and not as individual site data. In this case, a coordinating investigator will be designated by mutual agreement.

Authorship will be determined by mutual agreement and in line with International Committee of Medical Journal Editors authorship requirements.

Appendix B Adverse event definitions and additional safety information

B 1 Definition of adverse events

An adverse event is the development of any untoward medical occurrence in a subject or clinical study subject administered a medicinal product and which does not necessarily have a causal relationship with this treatment. An AE can therefore be any unfavourable and unintended sign (e.g. an abnormal laboratory finding), symptom (for example nausea, chest pain), or disease temporally associated with the use of a medicinal product, whether or not considered related to the medicinal product.

The term AE is used to include both serious and non-serious AEs and can include a deterioration of a pre-existing medical occurrence. An AE may occur at any time, including run-in or washout periods, even if no Study treatment has been administered.

B 2 Definitions of serious adverse event

A serious adverse event is an AE occurring during any study phase (i.e., run-in, treatment, washout, follow-up), that fulfils one or more of the following criteria:

- Results in death
- Is immediately life-threatening
- Requires in-subject hospitalisation or prolongation of existing hospitalisation
- Results in persistent or significant disability or incapacity.
- Is a congenital abnormality or birth defect
- Is an important medical event that may jeopardise the subject or may require medical treatment to prevent one of the outcomes listed above.

B 3 Life threatening

‘Life-threatening’ means that the subject was at immediate risk of death from the AE as it occurred or it is suspected that use or continued use of the product would result in the subject’s death. ‘Life-threatening’ does not mean that had an AE occurred in a more severe form it might have caused death (e.g., hepatitis that resolved without hepatic failure).

B 4 Hospitalisation

Outpatient treatment in an emergency room is not in itself a serious AE, although the reasons for it may be (e.g., bronchospasm, laryngeal oedema). Hospital admissions and/or surgical operations planned before or during a study are not considered AEs if the illness or disease existed before the subject was enrolled in the study, provided that it did not deteriorate in an unexpected way during the study.

B 5 Important medical event or medical treatment

Medical and scientific judgement should be exercised in deciding whether a case is serious in situations where important medical events may not be immediately life threatening or result in death, hospitalisation, disability or incapacity but may jeopardize the subject or may require medical treatment to prevent one or more outcomes listed in the definition of serious. These should usually be considered as serious.

Simply stopping the suspect drug does not mean that it is an important medical event; medical judgement must be used.

- Angioedema not severe enough to require intubation but requiring iv hydrocortisone treatment
- Hepatotoxicity caused by paracetamol (acetaminophen) overdose requiring treatment with N-acetylcysteine
- Intensive treatment in an emergency room or at home for allergic bronchospasm
- Blood dyscrasias (e.g., neutropenia or anaemia requiring blood transfusion, etc.) or convulsions that do not result in hospitalisation
- Development of drug dependency or drug abuse

B 6 Intensity rating scale:

The grading scales found in the revised NCI CTCAE latest version will be utilised for all events with an assigned CTCAE grading. For those events without assigned CTCAE grades, the recommendation in the CTCAE criteria that converts mild, moderate and severe events into CTCAE grades should be used. A copy of the CTCAE can be downloaded from the Cancer Therapy Evaluation Program website (<http://ctep.cancer.gov>). The applicable version of CTCAE should be described clearly.

It is important to distinguish between serious and severe AEs. Severity is a measure of intensity whereas seriousness is defined by the criteria in Appendix B 2. An AE of severe intensity need not necessarily be considered serious. For example, nausea that persists for several hours may be considered severe nausea, but not a SAE unless it meets the criteria shown in Appendix B 2. On the other hand, a stroke that results in only a limited degree of disability may be considered a mild stroke but would be a SAE when it satisfies the criteria shown in Appendix B 2.

B 7 A Guide to Interpreting the Causality Question

When making an assessment of causality consider the following factors when deciding if there is a 'reasonable possibility' that an AE may have been caused by the drug.

- Time Course. Exposure to suspect drug. Has the subject actually received the suspect drug? Did the AE occur in a reasonable temporal relationship to the administration of the suspect drug?

- Consistency with known drug profile. Was the AE consistent with the previous knowledge of the suspect drug (pharmacology and toxicology) or drugs of the same pharmacological class? Or could the AE be anticipated from its pharmacological properties?
- De-challenge experience. Did the AE resolve or improve on stopping or reducing the dose of the suspect drug?
- No alternative cause. The AE cannot be reasonably explained by another aetiology such as the underlying disease, other drugs, other host or environmental factors.
- Re-challenge experience. Did the AE reoccur if the suspected drug was reintroduced after having been stopped? AstraZeneca would not normally recommend or support a re-challenge.
- Laboratory tests. A specific laboratory investigation (if performed) has confirmed the relationship.

In difficult cases, other factors could be considered such as:

- Is this a recognized feature of overdose of the drug?
- Is there a known mechanism?

Causality of ‘related’ is made if following a review of the relevant data, there is evidence for a ‘reasonable possibility’ of a causal relationship for the individual case. The expression ‘reasonable possibility’ of a causal relationship is meant to convey, in general, that there are facts (evidence) or arguments to suggest a causal relationship.

The causality assessment is performed based on the available data including enough information to make an informed judgment. With limited or insufficient information in the case, it is likely that the event(s) will be assessed as ‘not related’.

Causal relationship in cases where the disease under study has deteriorated due to lack of effect should be classified as no reasonable possibility.

B 8 Medication Error

For the purposes of this clinical study a medication error is an unintended failure or mistake in the treatment process for an AstraZeneca study drug that either causes harm to the participant or has the potential to cause harm to the participant.

A medication error is not lack of efficacy of the drug, but rather a human or process related failure while the drug is in control of the study site staff or participant.

Medication error includes situations where an error.

- occurred

- was identified and intercepted before the participant received the drug
- did not occur, but circumstances were recognized that could have led to an error

Examples of events to be reported in clinical studies as medication errors:

- Drug name confusion
- Dispensing error e.g. medication prepared incorrectly, even if it was not actually given to the participant
- Drug not administered as indicated, for example, wrong route or wrong site of administration
- Drug not taken as indicated e.g. tablet dissolved in water when it should be taken as a solid tablet
- Drug not stored as instructed e.g. kept in the fridge when it should be at room temperature
- Wrong participant received the medication (excluding interactive voice response system [IVRS] / interactive web response system [IWRS] errors)
- Wrong drug administered to participant (excluding IVRS/IWRS errors)

Examples of events that **do not** require reporting as medication errors in clinical studies:

- Errors related to or resulting from IVRS/IWRS - including those which lead to one of the above listed events that would otherwise have been a medication error
- Participant accidentally missed drug dose(s) e.g. forgot to take medication
- Accidental overdose (will be captured as an overdose)
- Participant failed to return unused medication or empty packaging
- Errors related to background and rescue medication, or standard of care medication in open label studies, even if an AZ product

Medication errors are not regarded as AEs but AEs may occur as a consequence of the medication error.

Appendix C Handling of Human Biological Samples

C 1 Chain of custody of biological samples

A full chain of custody is maintained for all samples throughout their lifecycle.

The Investigator keeps full traceability of collected biological samples from the subjects while in storage at the centre until shipment or disposal (where appropriate).

The sample receiver keeps full traceability of the samples while in storage and during use until used or disposed of or until further shipment and keeps documentation of receipt of arrival.

AstraZeneca will keep oversight of the entire life cycle through internal procedures, monitoring of study sites, auditing or process checks, and contractual requirements of external laboratory providers

Samples retained for further use will be stored in the AZ-assigned biobanks and will be registered by the AstraZeneca Biobank Team during the entire life cycle.

C 2 Withdrawal of Informed Consent for donated biological samples

If a subject withdraws consent to the use of donated biological samples, the samples will be disposed of/destroyed, and the action documented. If samples are already analysed, AstraZeneca is not obliged to destroy the results of this research.

As collection of the biological sample(s) is an integral part of the study, then the subject is withdrawn from further study participation.

The Investigator:

- Ensures subjects' withdrawal of informed consent to the use of donated samples is notified immediately to AstraZeneca
- Ensures that biological samples from that subject, if stored at the study site, are immediately identified, disposed of /destroyed, and the action documented
- Ensures the organization(s) holding the samples is/are informed about the withdrawn consent immediately and that samples are disposed of/destroyed, the action documented and the signed document returned to the study site
- Ensures that the subject and AstraZeneca are informed about the sample disposal.

AstraZeneca ensures the organizations holding the samples is/are informed about the withdrawn consent immediately and that samples are disposed of/destroyed and the action documented and returned to the study site.

C 3 International Airline Transportation Association (IATA) 6.2 Guidance Document

LABELLING AND SHIPMENT OF BIOHAZARD SAMPLES

International Airline Transportation Association (IATA) classifies biohazardous agents into 3 categories. For transport purposes the classification of infectious substances according to risk groups was removed from the Dangerous Goods Regulations in the 46th edition (2005).

Infectious substances are now classified either as Category A, Category B or Exempt. There is no direct relationship between Risk Groups and Categories A and B.

Category A Infectious Substances are infectious substances in a form that, when exposure to it occurs, is capable of causing permanent disability, life-threatening or fatal disease in otherwise healthy humans or animals. Category A pathogens are e.g., Ebola, Lassa fever virus:

- are to be packed and shipped in accordance with IATA Instruction 602.

Category B Infectious Substances are infectious Substances that do not meet the criteria for inclusion in Category A. Category B pathogens are e.g., Hepatitis A, B, C, D, and E viruses, Human immunodeficiency virus types 1 and 2. They are assigned the following UN number and proper shipping name:

- UN 3373 – Biological Substance, Category B
- are to be packed in accordance with UN3373 and IATA 650

Exempt - all other materials with minimal risk of containing pathogens

- Clinical trial samples will fall into Category B or exempt under IATA regulations
- Clinical trial samples will routinely be packed and transported at ambient temperature in IATA 650 compliant packaging
- **Biological samples transported in dry ice require additional dangerous goods specification for the dry-ice content**
- IATA compliant courier and packaging materials should be used for packing and transportation and packing should be done by an IATA certified person, as applicable
- Samples routinely transported by road or rail are subject to local regulations which require that they are also packed and transported in a safe and appropriate way to contain any risk of infection or contamination by using approved couriers and packaging/containment materials at all times. The IATA 650 biological sample containment standards are encouraged wherever possible when road or rail transport is used.

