6.6.2 Definition of dose-limiting toxicity and evaluable subject

DLT evaluable patients are defined as those who received 2 planned doses of MEDI9447 per protocol during the DLT assessment period and completed the safety follow-up through the DLT assessment period, or those who experienced a DLT. Also, the period for DLT evaluation is defined as the time from receiving the first dose of investigational product until assessments prior the planned administration of the third dose; this corresponds to 28 days after receiving the first dose of the investigational product or 14 days after the second dose, whichever occurs later (defined as Cycle 1). Subjects who do not remain in the study up to this time for reasons other than DLT will be considered non-evaluable for DLT assessment and will be replaced with another subject at the same dose level. In case of discontinuation from or interruption of treatment due to AE during the DLT evaluation period (e.g., \geq grade 3 IRR), whether the AE should be a DLT will be discussed by the SRC based on the below mentioned DLT definition 11. Grading of DLTs will be according to the NCI CTCAE v4.03.

A DLT will be defined as any of the events listed below that occurs during the DLT-evaluation period (defined above). Toxicity that is clearly and directly related to the primary disease or to another etiology is excluded from this definition. The following will be DLTs:

- 1 Grade 4 immune-mediated adverse event (imAE)
- 2 \geq Grade 3 colitis
- 3 \geq Grade 3 nausea, vomiting, or diarrhea that does not resolve to Grade 2 or less within 3 days of the initiation of maximal supportive care
- 4 \geq Grade 3 pneumonitis or ILD
- 5 Grade 4 anemia or anemia requiring red cell transfusion
- 6 Grade 4 thrombocytopenia or neutropenia that is present for more than 4 days
- 7 Grade 3 thrombocytopenia with bleeding or thrombocytopenia requiring platelet transfusion

- 8 Febrile neutropenia
- 9 Isolated liver transaminase elevation $\geq 5 \times$ but $\leq 8 \times$ ULN or isolated total bilirubin $\geq 3 \times$ but $\leq 5 \times$ ULN that does not downgrade to Grade 2 or less within 14 days after onset with optimal medical management, including systemic corticosteroids. Isolated liver transaminase elevation $> 8 \times$ ULN or isolated total bilirubin $> 5 \times$ ULN regardless of duration.

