7.1.1 Procedures for discontinuation of study treatment

A subject that decides to discontinue Study treatment will always be asked about the reason(s) and the presence of any AEs at the time of study treatment discontinuation. The date of last administration of Study treatment should be documented in the eCRF. Subjects permanently discontinuing Study treatment should be given clinically available care therapy, at the discretion of the Investigator.

Discontinuation of Study treatment, for any reason, does not impact on the subject's participation in the study. The subject should continue attending subsequent study visits and data collection should continue according to the study protocol. If the subject does not agree to continue in-person study visits, a modified follow-up must be arranged to ensure the collection of endpoints and safety information. This could be a telephone contact with the subject, a contact with a relative or treating physician, or information from medical records. The approach taken should be recorded in the medical records. A subject that agrees to modified follow-up is not considered to have withdrawn consent or to have withdrawn from the study.

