7.3 Withdrawal from the study

A subject may withdraw from the study (e.g., withdraw consent), at any time (investigational product **and** assessments) at his/her own request, without prejudice to further treatment.

A subject who considers withdrawing from the study must be informed by the Investigator about modified follow-up options (e.g., telephone contact, a contact with a relative or treating physician, or information from medical records).

If the subject withdraws consent for disclosure of future information, the sponsor may retain and continue to use any data collected before such a withdrawal of consent.

If a subject withdraws from the study, he/she may request destruction of any samples taken, and the investigator must document this in the site study records.

A subject who withdraws consent will always be asked about the reason(s) and the presence of any AE. The Investigator will follow up subjects as medically indicated.

See [Table 3](#), for data to be collected at the time of study discontinuation and follow-up and for any further evaluations that need to be completed.

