8.5.2 Storage and destruction of pharmacokinetic samples

PK samples will be stored for a maximum of 15 years from the date of the Last Subject's Last Visit, after which they will be destroyed.

After PK analysis, remaining PK samples may be used for biomarker analysis. The results of this research will be reported either in the CSR itself or as an addendum, or separately in another report or a scientific report or publication.

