8.8 Biomarkers

By participating in this study, the subject consents to the collection and use of donated biological samples as described here.

The below samples for biomarker research are required and will be collected from all subjects in this study as specified in the SoA.

To explore the relationship(s) between biomarker status and PK of MEDI9447, clinical outcomes, efficacy, AEs, and/or safety parameters, an archival tumor tissue, whole and plasma blood samples and/or serum samples (for biomarkers including but not limited to sCD73) are tested.

Adequate tumor tissue is defined as a formalin-fixed and paraffin-embedded (FFPE) tumor block or approximately 10 unstained slides, each 4 to 5 microns thick. An archival FFPE sample taken within 3 years prior to screening is preferred.

Blood samples will be taken as specified in the SoA. An approximately 3.5 mL whole blood sample will be collected at each time point, and more than 0.5 mL of serum sample will be obtained from it.

Instructions for the collection and handling of biological samples will be provided by the sponsor or analytical test site.

CCI

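### Appendix C 2 removes from the study a subject who withdraws only consent to sample use, without protecting the scheduled safety follow-up that subject may still be willing to give

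*Supplement*

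**What the plan says.** Appendix C 2 names a narrow trigger: "If a subject withdraws consent to the use of donated biological samples, the samples will be disposed of/destroyed, and the action documented". The consequence is wide: "As collection of the biological sample(s) is an integral part of the study, then the subject is withdrawn from further study participation". C 2 mentions neither adverse event collection nor Section 7.

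Section 8.8 uses the term donated biological samples for the biomarker samples and makes them compulsory: "The below samples for biomarker research are required and will be collected from all subjects in this study as specified in the SoA". Section 3 (Table 4) lists safety, tolerability and DLTs as the primary objective. PK, immunogenicity and archival tumor biomarkers are secondary, and relationships with biomarker status are exploratory.

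Section 7.1.1 takes a different line when a subject stops treatment. Participation goes on, and if in-person visits are refused, "a modified follow-up must be arranged to ensure the collection of endpoints and safety information". A subject who accepts this is expressly not counted as withdrawn from the study.

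Section 7.3 covers withdrawal from the study at the subject's own request. It provides that "A subject who considers withdrawing from the study must be informed by the Investigator about modified follow-up options", asks for the reason and any adverse event, states that "The Investigator will follow up subjects as medically indicated", and refers to Table 3 for further data collection. Table 3 schedules adverse event assessment at 30 and 90 days after the last dose, and serum chemistry and hematology at 30 days.

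For DLT assessment, Section 6.6.2 says: "Subjects who do not remain in the study up to this time for reasons other than DLT will be considered non-evaluable". Such a subject is replaced at the same dose level.

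**The concern.** The trigger and the consequence do not match. The ground given in C 2 is that sample collection is integral to the study, but what the subject has withdrawn is consent to use. A subject can object to use and still accept every safety visit. C 2 treats that subject as having left altogether.

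Two things are at stake. Within the DLT period, a subject without a DLT who leaves becomes non-evaluable, and one more patient is exposed as a replacement, although Section 9.2 aims to expose as few subjects as possible. After that period, scheduled adverse event collection may end early, although Sections 6.6.1 and 6.6.2 ask the Safety Review Committee to consider late-emerging immune-mediated events, which this follow-up would supply. Both bear on the primary objective, and the cause is a consent decision about secondary and exploratory material.

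**Working it through.** The point rests mainly on reading the sections together. The arithmetic only gives the scale.

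**1. Does another section restore follow-up for this subject?**

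| Section | Who it covers | Effect |
|---|---|---|
| Appendix C 2 | withdraws consent to sample use | removed from the study by rule; no safety exception, no cross-reference |
| 7.1.1 | stops study treatment | stays in the study; modified follow-up required if visits are refused |
| 7.3 | asks, or considers asking, to leave (product and assessments) | told of modified follow-up, asked about AEs, followed as medically indicated, Table 3 cited |

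The C 2 subject has not asked to stop treatment or assessments, so neither 7.1.1 nor 7.3 clearly applies. The status rules also conflict: under 7.1.1 a subject on modified follow-up has not withdrawn, while under C 2 this subject has. One site could reasonably end adverse event collection and another continue it to day 90.

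**2. The plan's own figure.** The synopsis gives a maximum of 12 evaluable patients: 2 cohorts × 6 = 12, which reproduces. The maximum is unaffected, because non-evaluable subjects are replaced.

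**3. Weight of one subject.** 1/3 = 33% of a cohort of 3; 1/6 = 17% of a cohort of 6; 1/12 = 8% of the maximum.

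**4. Effect on the 3+3 decision.** Let p be the DLT rate and q = 1 − p. A cohort passes with 0 of 3 DLTs, or with 1 of 3 followed by 0 of 3:

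P(pass) = q³ + 3p·q²·q³

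For p = 0.2: 0.512 + 3 × 0.2 × 0.64 × 0.512 = 0.709.

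If a fraction w leaves before a DLT is seen, independently of toxicity, the DLT rate among evaluable subjects is p(1 − w)/[p(1 − w) + q(1 − w)] = p, so nothing changes. In the extreme opposite case, where only subjects who would have had a DLT leave, the rate falls to p(1 − w)/[p(1 − w) + q].

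| Assumed p | P(pass), no withdrawal or independent withdrawal | Extreme case, w = 10% | Extreme case, w = 20% |
|---|---|---|---|
| 10% | 0.906 | 0.921 | 0.935 |
| 20% | 0.709 | 0.744 | 0.780 |
| 30% | 0.494 | 0.539 | 0.588 |
| 40% | 0.309 | 0.351 | 0.401 |

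The values of p and w are assumptions; the protocol gives neither. The last two columns show what toxicity-related withdrawal would do. Nothing in the documents suggests that withdrawal of sample consent is of that kind.

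**The case against.** The best defence is that Appendix C governs samples and Section 7.3 governs withdrawal, so follow-up is already handled there. Samples are also a condition of entry: inclusion criterion 5 requires tumor tissue, and Section 6.6.3 has the Safety Review Committee review PK as well as safety data. Making samples integral is thus a deliberate choice with a stated reason.

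Much of this stands. It rules out several stronger readings that a reader might infer:

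- **That primary safety data are lost, or the patient is left without any safety follow-up.** Section 7.3 provides real safeguards. Every dosed subject stays in the safety analysis set (Section 9.3). What is missing is a statement that the scheduled follow-up applies to a subject removed under C 2.
- **That the dose decision is biased.** Non-evaluable subjects are replaced, and a DLT already seen still counts. If withdrawal is unrelated to toxicity, the pass probability is unchanged.
- **That refusing re-use of leftover PK serum, or long storage, triggers the rule.** Section 8.5.2 says only "After PK analysis, remaining PK samples may be used for biomarker analysis". It does not call that serum donated, and it does not link refusal to C 2.
- **That softer wording would keep the subject DLT-evaluable.** Without a DLT, Section 6.6.2 also requires 2 planned doses, so this depends on what happens to treatment.

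The defence does not close the gap. Section 7.3 is written for a subject who wishes to leave, and C 2 removes one who may not. Making samples a condition of entry does not explain why safety visits should stop for someone already dosed.

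**Conclusion.** The point holds as a narrow one. C 2 ends participation for a reason unrelated to safety and leaves scheduled safety follow-up unprotected: adverse events to 90 days after the last dose, and serum chemistry and hematology at 30 days. Section 7.3 mitigates this but does not clearly reach the subject concerned.

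The impact is low. For each affected subject, the exposure is at most the remaining scheduled follow-up, plus one replacement patient if it happens in the DLT period without a DLT. In a cohort of 3 to 6, that subject is 33% to 17% of the cohort. The documents give no rate of sample-consent withdrawal, and it is likely low. The conclusion that the 3+3 decision is unbiased assumes that such withdrawals are independent of toxicity.

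**What to change.** Amend Appendix C 2 along these lines: withdrawal of consent to the use of donated samples stops the affected sampling and use. Unless the subject also withdraws consent to follow-up, AE/SAE and safety laboratory follow-up continue as scheduled in Table 3, with AE/SAE collection through 90 days after the last dose, and the modified follow-up options of Sections 7.1.1 and 7.3 are offered.

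C 2 must also be reconciled with Section 7 on whether study treatment continues for this subject. The protocol does not settle that, and no answer is proposed here. For the reason given above, the amendment should not claim that DLT evaluability is preserved.

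The cost is amendment and consent-form wording, and some missing biomarker or PK values for that subject.
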